The aims of the study are to (1) Determine the feasibility and acceptability of Wits Workout among 120 intervention group recipients who receive the program at 8 locations in Illinois; and (2) Use a randomized trial to examine the preliminary efficacy of Wits Workout on changes in the primary outcomes of cognitive functioning, and secondary outcomes of self-efficacy, socialization, sleep, stress and physical activity levels following the 12-week intervention (3 months) and explore maintenance effects at 6 months (3-months post-intervention) compared to a waitlist control.

Hypotheses: At three and six-month posttests, intervention participants compared to controls will differentially improve with respect to (1) PROMIS^{6,7} self-reported cognitive function measures; (2) scores on the Telephone Interview for Cognitive Screening (TICS); and (3) self-efficacy, socialization, sleep, stress and physical activity levels.

Research Design

We propose to conduct a two-arm randomized controlled trial with a treatment (workshop) group and wait-list control group. We will assess participant outcomes at baseline, immediately post-workshop (3-months) and at 6-months to assess maintenance of treatment effects.

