Intervention. Wits Workout will take place over 12 weeks, one hour per week. The training will be delivered by 5 UI Extension faculty educators who were trained by the Extension faculty educators who developed the program. Each week includes a themed module with four activities and a training component featuring educational topics such as a) exercising regularly; c) engaging the brain with new and intellectually stimulating challenges; d) participating in social activities; e) getting enough sleep; and f) reducing stress. The workshop will be offered in-person in 8 areas with a target of 20 attendees per urban workshop and 12 attendees per rural workshop for a total of 120 workshop participants. The waitlist control participants (n=120) will be offered the workshop after the 6-month study period is completed. All COVID safety requirements will be in place at the workshop sites. A fidelity assessment tool will be developed by the research team and implemented at all program sites. All Wits Workout leaders will be observed teaching two sessions of the program by one of the study investigators. After the first observation occurs, the fidelity evaluator will debrief with the leader and the evaluator will follow up with a written evaluation that includes strengths, areas of improvement (including ways in which they adhered and/or strayed from the program content and facilitation techniques outlined in the Wits Workout Leader's Guide), and suggestions for increasing fidelity in their teaching. A second observation will occur within the several weeks of the first observation with the goal of continuous process improvement from the first

to the second evaluation. UI faculty educators leading the workshops will record attendance over the 12 weeks and report to the investigative team. Attrition as well as completion rates will be documented based on workshop attendance.

Sample. We will offer Wits Workout to a minimum of 240 older adults (120 treatment and 120 delayed treatment controls) in three urban and five rural areas of Illinois (see

Location	Urban/Rural	Numbers	Waitlist
Chicago Area	Urban	20	20
Chicago Area	Urban	20	20
Champaign	Urban	20	20
St. Joe/Paxton	Rural	12	12
Sterling	Rural	12	12
Mattoon	Rural	12	12
Macomb	Rural	12	12
Marion	Rural	12	12
Total Participants		120	120

Table 1).

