baseline assessment is completed, participants will be randomized into two groups by a member of the research team. The treatment group will receive the 12-week workshop and the waitlist control group will receive the treatment after the six-month posttest is complete (see Figure 1). The first posttest and TICS will be administered by a member of the research team to both the workshop and control groups immediately following the end of the 12-week program (3 months). The 6-month follow-up assessment and TICS will be administered 3 months after the end of the program to both the workshop and control groups by a member of the research team. Reminders to complete the survey will be sent by a research team member by email and/or phone. Participants will be provided a \$20 gift card upon completion of each survey that will be administered by a research assistant. A "reunion" event will take place three months after the last *Wits Workout* session for the workshop group only. The reunion will give participants an opportunity to reconnect informally and it will enable the research team to conduct the follow-up focus groups. Qualitative methods are particularly well suited for the assessment of simulated changes in behavior and will provide us richer detail than the surveys alone¹⁶.

Power Analysis and Sample Size Estimation. In the cognition literature, a 1-3 point decrease in the Mini Mental State Exam score has been shown to be indicative of a meaningful decline. Our primary outcome, cognitive functioning, will be assessed using the TICS -- a telephone version of Mini Mental State Exam which is administered in person. Both measures correlate highly.^{9,10} Among older adults with normal cognition, which is our target sample for this trial, an effect size of 0.29 was considered clinically meaningful.¹¹ With this more conservative effect size of .20, an alpha of .05/6 = 0.008 9adjusted for multiple outcome measures and comparisons across rural and urban samples), for 3 time points (0-12-24 weeks), power set to .80, and an estimated correlation of .50 among measures, we need a total of 208 participants. Accounting for ~15% attrition, we will target to recruit a total of 240 participants for this trial. **Data Analysis**

Quantitative data. We will conduct 3x2 repeated measures ANOVAs to examine time (pre vs. post vs. follow-up),

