group (intervention vs. waitlist control), and interaction effects. The quantitative measures that will be evaluated using this statistical model include measures of social satisfaction and support, perceived well-being and quality of life, physical activity and exercise, self-efficacy, and the cognitive functioning scores. Covariates such as demographics [age, biological sex, geographic location (rural vs. urban)], and attendance to the Wits Workout program will be accounted for in the analyses. As a secondary analysis, we will also examine correlations between the demographic characteristics and the study outcomes. Drs. [name] and [name] have experience in analyzing similar large datasets from randomized controlled trials using these analysis strategies.

Qualitative data. [name] will conduct the focus groups using a guide to facilitate the discussion. The guide will include nine questions that will provide more in-depth detail about outcomes experienced by the participants (i.e. *In what ways did participating in Wits Workout impact your health behaviors?*) as well as questions that will provide details about their perception of the program (i.e. *What suggestions do you have to improve the program?*). We will audiotape and transcribe the focus groups. Three research team members will review all transcripts to develop an initial code book. We will then apply the codebook to a subsample of the transcripts individually then meet to discuss any areas where we are not coding consistently and adjust the codebook accordingly. We will then apply the same technique to another subsample of transcripts. Once we are certain that coding is consistent and the codebook is finalized, [name] will code the transcripts using NVivo QSR qualitative software. She will use an inductive thematic analysis process to analyze the data. Themes will be discussed and finalized with the research team.

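### Table 1 targets equal arms within each of eight sites, but randomisation is not tied to site and the model names only rural/urban: stratify by site and model it

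*Combined protocol and SAP*

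**What the plan says.** **Site numbers.** The Sample paragraph plans "a minimum of 240 older adults (120 treatment and 120 delayed treatment controls) in three urban and five rural areas of Illinois". Table 1 lists the eight locations with the same number in the workshop and waitlist columns of every row, for example "Sterling Rural 12 12". The Intervention paragraph describes the workshop sizes as "a target of 20 attendees per urban workshop and 12 attendees per rural workshop".

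**Allocation.** The design is a "two-arm randomized controlled trial with a treatment (workshop) group and wait-list control group". Under Procedures, once baseline is complete, "participants will be randomized into two groups by a member of the research team". No sequence method, blocking or stratification is given, either by site or by rural/urban.

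**Analysis.** Data Analysis specifies a 3x2 repeated measures ANOVA (time by group). The covariates are given as examples: age, biological sex, "geographic location (rural vs. urban", and attendance. No site term is named. The power section divides alpha by six, partly to allow for comparisons between rural and urban samples.

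**The concern.** The three parts do not fit together. Table 1 is a within-site plan, the randomisation sentence is a whole-trial statement, and the model works at a two-level grouping of the sites.

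There are two ways to read the allocation, and each has a cost. If it is unrestricted, the site split in Table 1 will almost never occur. Some workshops in an in-person, interactive programme will then be well above or below their intended size. If it is balanced within site, the analysis should carry the factor that was balanced. Otherwise stable site differences stay in the between-person error term although the design has already removed them from the arm comparison.

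**Working it through.** **Inputs.** Table 1: three sites of 40 (20/20) and five of 24 (12/12). Power section: effect size 0.20, alpha 0.008, power 0.80, three time points, correlation 0.50, N = 208. The documents give no figure for between-site variance, so a share v of single-visit variance from 0.02 to 0.10 is assumed.

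**1. The plan's own figure.** Read as Cohen's f for the between-group main effect, the noncentrality is λ = N·f²·m / (1 + (m−1)ρ) = 208 × 0.04 × 3 / 2 = 12.48. With 1 and 206 degrees of freedom and alpha 0.008, power is 0.802, so N = 208 reproduces. The group-by-time formula, λ = N·f²·m / (1−ρ), would need only 64. The sample size therefore rests on the main effect.

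**2. If allocation is unrestricted 1:1 and each site enrols its planned total.**
- Exact split: C(24,12)/2²⁴ = 0.161 for a rural site; C(40,20)/2⁴⁰ = 0.125 for an urban site.
- All eight exact: 0.1254³ × 0.1612⁵ = 2.1 × 10⁻⁷.
- Rural workshop assigned 15 or more: P(X ≥ 15), X ~ Binomial(24, 0.5), is 0.1537. At least one of five: 1 − 0.8463⁵ = 0.566.

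The chance that some site is off target (20,000 simulated allocations) is:

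| Allocation | Off by 3 or more | Off by 5 or more |
|---|---|---|
| Simple | 97% | 57% |
| Only the 120/120 total fixed | 94% | 45% |
| Rural/urban strata only | 88% | 32% |

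Stratifying by rural/urban alone therefore does not deliver Table 1. For a site-adjusted analysis, the variance cost of this imbalance is about 3%.

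**3. If allocation is balanced within site and site is left out of the model.** With three visits and ρ = 0.50, the variance of a person's mean is (1 + 2 × 0.50)/3 = 2/3 of the single-visit variance. A stable site share v therefore becomes v/(2/3) = 1.5v of the variance behind the main-effect test. The ratio of model SE to true SE is about (1 − 1.5v)^−½:
- v = 0.02: (0.97)^−½ = 1.015
- v = 0.10: (0.85)^−½ = 1.085

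The rural/urban covariate absorbs a little of this, so the upper value is slightly generous. Simulated trials at v = 0.05 to 0.10 gave ratios of 1.01 to 1.08, with rejection of 3.3% to 4.8% at a nominal 5%. Adding site brought the ratio to about 1.00.

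For the group-by-time contrast, stable site differences cancel in the change scores. The simulated ratio was 0.98 to 1.02 and rejection 4.5% to 5.7%, with Monte Carlo error of about 1% on the ratio.

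**4. If allocation is simple and only rural/urban is modelled.** The simulated ratio was 0.98 to 1.00 and rejection 4.8% to 5.5%, so the inference is valid.

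**The case against.** The site numbers are targets and 240 is a minimum. No workshop capacity is stated, so 15 assigned against 12 is a missed target and not a breached limit. The protocol does not say that allocation is unrestricted; Table 1 suggests the opposite, and then the probabilities in step 2 do not apply. The covariate list is open, so site could still be added. Chance imbalance between sites under randomisation is not bias. All of this stands, and it limits the point to a gap in specification with a modest cost.

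Three stronger readings are tempting, and the documents do not support them.

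- **That the standard errors are wrong in general.** They are valid under simple randomisation and essentially correct for group-by-time, which carries the hypothesis that the workshop group improves more than controls. Only the main effect is affected, and in the conservative direction. Leaving out site does not inflate false positives.
- **That leaving out site takes power below the planned 80%.** The power section does not say which SD standardises its effect size. If that SD includes site differences, leaving site out only forgoes a gain from balancing.
- **That arm is confounded with site.** Individual randomisation leaves only chance imbalance, at the cost of about 3% in variance.

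It is also fair to object that simply replacing rural/urban with site would lose a comparison the alpha was partly set for. The fix has to keep that comparison.

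**Conclusion.** The point holds as a mismatch between the site plan, the randomisation sentence and the model. Unrestricted allocation would practically never give the split in Table 1, and at least one rural workshop would probably (57%) be assigned 15 or more against 12. Those figures assume that every site enrols exactly its planned total.

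Under within-site balance, the cost of omitting site is confined to the group main-effect test: an SE about 1.5% to 8% too large. That range rests wholly on the assumed 2% to 10% site share and on the plan's own correlation of 0.50. N = 208 is not put in question by this point.

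Shared workshop effects within the intervention arm are a different matter. They act in the other direction, making standard errors too small, and a fixed site factor does not cure them. They need separate treatment.

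**What to change.** 1. In Procedures, state that participants are randomised 1:1 from a computer-generated permuted-block list stratified by site (eight strata, varied even block sizes). This gives 20/20 or 12/12 at sites that enrol in full with the last block complete, and a small difference otherwise.
2. In Data Analysis, include site as an 8-level fixed factor in place of the rural/urban main effect, which site already contains. Keep the planned rural/urban comparison as a group-by-rural/urban term, and its product with time.

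Cost: a list and one model term. Site uses 7 degrees of freedom where rural/urban used 1, so 6 more out of about 200. The sample size does not change.

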Qualitative Outcomes. We will conduct focus groups with participants 3 months after the conclusion of the workshops to learn more about the impact of the workshop on participant's health behaviors and their thoughts about how the program was delivered and evaluated.

[figure not shown]
Outcome Measures. We will examine the effects of participation in Wits Workout on the primary outcome of cognitive functioning and secondary outcomes of improved social satisfaction, self-efficacy, quality of life and sleep, reduced stress, and increased physical activity using the following measurements: Cognitive functioning will be assessed using the PROMIS Cognitive Function- Short Form 8a^{6,7} and the Telephone Interview for Cognitive Status (TICS). ^{8,9} TICS is a brief, standardized test of cognitive functioning designed to be measured over the telephone. Social-satisfaction will be assessed using the Cutrona Social Provisions Scale¹⁰. Self-efficacy will be assessed using the PROMIS Item Bank v1.0 - General Self-Efficacy. ⁶ Sleep will be assessed using the Pittsburg Sleep Quality Index (PSQI).¹³ Stress will be assessed using the Perceived Stress Scale.¹⁴ Physical activity will be assessed using the Physical Activity Scale for the Elderly (PASE).¹⁵

Participant inclusion/exclusion criteria: 1) age 50+; 2) English speaking /understands English; 3) No self-reported serious mental illness or diagnosis of Alzheimer's or other dementia related disease, and a score of 27 or higher on the TICS cognitive assessment during the screening call.

Procedures

Participants will be recruited through UI Extension utilizing community partners, the Extension website, Extension newsletters, and multiple media outlets, including news releases, fliers, and social media. Upon registering for the program, participants will be contacted and invited to take part in the research study. Those interested will be screened

for inclusion into the study with a brief telephone interview which includes the TICS assessment. Participants who are eligible will be sent a consent form and baseline assessment. University of Illinois at Chicago will provide institutional review board approval. All survey assessments will be administered online unless a participant is unable to complete the survey online in which case s/he will be offered the opportunity to take the survey via phone with a researcher or to receive a paper copy with a selfaddressed, stamped return envelope. Once the

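### The workshop-only reunion and focus groups fall at the same nominal time as the 6-month assessment, with no order stated in the readable text, so some 6-month self-reports could follow a contact that controls do not get

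*Combined protocol and SAP*

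**What the plan says.** Four statements in the combined protocol and SAP bear on the timing.

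- **6-month assessment, both arms (Procedures):** "The 6-month follow-up assessment and TICS will be administered 3 months after the end of the program".
- **Reunion (Procedures):** it is placed three months after the last "session for the workshop group only. The reunion will give participants an opportunity to reconnect informally". Of the same event the section says that "it will enable the research team to conduct the follow-up focus groups".
- **Focus groups (Qualitative Outcomes):** "We will conduct focus groups with participants 3 months after the conclusion of the workshops to learn more about the impact". The topics also include "their thoughts about how the program was delivered and evaluated".
- **Waitlist workshop (Procedures):** "the waitlist control group will receive the treatment after the six-month posttest is complete (see Figure 1").

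Two further statements in Procedures govern how the surveys are collected: "All survey assessments will be administered online unless a participant is unable to complete the survey online", and "Reminders to complete the survey will be sent by a research team member by email and/or phone". Phone and paper are the alternatives to the online form. No earliest or latest date for the 6-month survey is given.

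Overall Aims treats the 6-month comparison as an exploration of whether effects last. Hypotheses nevertheless predicts a benefit over controls at both 3 and 6 months.

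**The concern.** The 6-month comparison is meant to show what remains of the program's effect after three months without it. The reunion brings workshop participants back together, and the focus groups ask them how the program changed their health behaviors. Controls have no matching event before their own 6-month assessment. If part of the workshop arm answers the 6-month survey after that event, the arm difference contains both what was maintained since the program and any short-term lift from the reunion. The planned data could not separate the two, and an effect that had faded could look partly maintained.

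**Working it through.** No figure in the plan measures this point, so the check is a comparison of the timing statements.

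| Event | Who | Stated time | Stated order or window |
|---|---|---|---|
| 6-month survey and TICS | Both arms | Three months after the program ends | None |
| Reunion | Workshop arm only | Three months after the last session | None |
| Focus groups | Held at the reunion | Three months after the workshops end | None |
| Waitlist workshop | Control arm | After the six-month posttest | Yes: the posttest must be complete |

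1. **The times coincide.** The last session is the end of the program, so the first three rows share one nominal date. The only ordering rule concerns the control arm's later workshop.

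2. **Overlap is realistic.** A reunion takes place on a set day. Online surveys with reminders come in over a period, and no cut-off is stated. Followed as written, the plan allows some surveys to be completed before the reunion and some after it.

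3. **The extra contact is in one arm only.** The reunion and its focus groups are for the workshop group.

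4. **The contact bears on what is measured.** Meeting again socially is close to what the Social Provisions Scale asks about. The focus-group guide, under Qualitative data, asks about effects on health behaviors, which touches sleep and physical activity. The self-reports of cognition (PROMIS), self-efficacy and stress could also be colored by a group discussion of the program's benefits. The TICS is a standardized test and is less exposed, although its order relative to the reunion is equally unstated.

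5. **Which comparisons are touched.** The 3-month assessment takes place before any reunion, so the direct 3-month comparison is clean. Only 6-month data are exposed. Because follow-up is one of the three time levels in the planned 3x2 repeated measures ANOVA, a shift at 6 months would also enter that model's overall group and interaction tests.

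6. **Size.** Any bias depends on the share of the workshop arm that answers after attending and on how far their answers move as a result. The documents give neither, nor expected reunion attendance. A number would only return whatever was assumed, so none is offered. If all assessments come first, the bias is exactly zero.

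**The case against.** The best reply is that the intended order is probably assessment first.

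- Procedures runs in sequence from baseline through the 3-month and 6-month assessments to the reminders, and describes the reunion last.
- A focus group on how the program was evaluated makes most sense once participants have been assessed.
- The research team both administers the assessments and runs the focus groups, so it can control the order.
- Figure 1, cited in the sentence that orders the waitlist workshop, may show the sequence.

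All of this is fair, and it makes a large share of late answers less likely. It is still not a rule: order of narration does not stop an online survey from being returned after a reunion held on the same nominal date. If Figure 1 does settle the order, what remains is to repeat it in the text.

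It is also fair that the reach is narrow. The exposure is mainly in self-reports, at a time point that the aims call exploratory, in a trial of preliminary efficacy. That lowers the priority. It does not remove the point, because the hypotheses name 6 months and PROMIS cognition belongs to the primary outcome domain.

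A third objection is practical: holding a reunion until every last survey is in would let one late responder delay a whole site. That stands, and it is why the remedy needs a fixed closing date.

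**Conclusion.** The point holds as a minor one with a cheap improvement. In the readable text, a contact given to one arm shares a nominal time with the 6-month assessment, with no order and no window. Some workshop-arm self-reports could therefore be given after it, and a reunion effect could not be separated from maintenance.

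A reader might infer that the 6-month result is biased, or that the plan puts the reunion before the assessment. The documents support neither: they state no order, and the bias is possible rather than shown. A reader might also infer that the trial's main result is at risk. The direct 3-month comparison is unaffected, and the TICS, the measure named in the power calculation, is less exposed.

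The conclusion assumes that Figure 1 does not already fix the order and that survey completion dates will spread around the nominal date, as online collection with reminders suggests. The size of any bias cannot be estimated from the documents.

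**What to change.** 1. Set one 6-month assessment window for the survey and TICS, with a fixed closing date and the same rule in both arms. The documents give no length, so the investigators must choose it.
2. Schedule each site's reunion and focus groups after that window closes. The plan already uses completion of the six-month posttest as the milestone for the waitlist workshop; this applies the same idea to the workshop arm's extra contact.
3. Amend the three-month timing of the reunion and focus groups in Procedures and Qualitative Outcomes to match.
4. Record the date of each assessment and of each reunion.
5. Keep late responses in the main analysis and report how many workshop-arm assessments followed the reunion. Any analysis that leaves them out is supporting only, because the exclusion is selective and made in one arm.
6. If Figure 1 already gives this order, state it in the text.

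The cost is a scheduling rule, two matching text edits and some recorded dates. The reunion and focus groups move back by the length of the window, so participants recall the program over a slightly longer period. No assessment data are lost.

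### Opinions of the program are sought only in focus groups tied to a reunion, so the acceptability conclusion for the 120 recipients may lean favourable and miss reasons for stopping.

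*Combined protocol and SAP*

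**What the plan says.** Under Overall Aims, the first of the two aims is to "Determine the feasibility and acceptability of Wits Workout among 120 intervention group recipients who receive the program at 8 locations in Illinois". The Intervention paragraph gives the make-up of that group: "20 attendees per urban workshop and 12 attendees per rural workshop for a total of 120 workshop participants".

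Three places describe how participants' views will be gathered:

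- **Qualitative Outcomes:** "We will conduct focus groups with participants 3 months after the conclusion of the workshops". The topics are effects on health behaviours and "their thoughts about how the program was delivered and evaluated".
- **Procedures:** the reunion takes place three months after the last "session for the workshop group only". Besides its social purpose, "it will enable the research team to conduct the follow-up focus groups".
- **Data Analysis, Qualitative data:** the guide has questions on outcomes "as well as questions that will provide details about their perception of the program". Transcripts are coded and analysed by theme.

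Two other parts bear on the aim. The Intervention paragraph has workshop leaders record attendance over the 12 weeks, from which attrition and completion are documented. Outcome Measures lists the survey instruments and the TICS. They cover cognition, social provisions, self-efficacy, sleep, stress and physical activity; none is a measure of satisfaction or acceptability.

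**The concern.** Acceptability is one of only two aims and is stated for everyone who receives the workshop. Someone who stopped after a few weeks has less reason than a regular attender to come to a social event three months after the series ends. If the groups are formed from those who come, the views collected will tend to be those of people who stayed and were content.

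The likely direction is favourable to the program. The likely gap is in what a feasibility and acceptability aim most needs to learn, namely why people stopped. The randomised comparison of cognitive and other outcomes is not affected.

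**Working it through.** **1. The denominator.** Table 1 has three urban sites of 20 and five rural sites of 12: 3 × 20 + 5 × 12 = 60 + 60 = 120. This agrees with the 120 in Aim 1, so the aim covers the whole workshop arm and not completers only.

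**2. What each planned source can say about acceptability.**

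| Source | Who is covered | Opinion of the program? | Reason for stopping? |
|---|---|---|---|
| Attendance, attrition, completion | Whole workshop arm | No | No |
| 3- and 6-month surveys and TICS | Both arms, with reminders | No item listed | No item listed |
| Focus groups | Participants; no sampling rule, number of groups or group size given | Yes | Possible, if leavers take part |

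Only the last row collects opinions, and it is the row whose coverage is undefined and tied to the reunion. No exit interview or other route to people who left is described.

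**3. How large a gap could be.** The plan defines no acceptability rate, so this is an illustration only. Let *d* be the share of recipients not heard, *p_h* acceptability among those heard, and *p_l* acceptability among those who left and are not heard.

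- All recipients: (1 − *d*) × *p_h* + *d* × *p_l*
- Gap between those heard and all recipients: *d* × (*p_h* − *p_l*)

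All three inputs are assumed. The value *d* = 0.15 (0.15 × 120 = 18 people) borrows the figure under Power Analysis and Sample Size Estimation. That figure is study attrition; the documents give none for leaving the workshop. With *p_h* = 0.90:

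| *p_l* | All recipients | Gap |
|---|---|---|
| 0.80 | 0.85 × 0.90 + 0.15 × 0.80 = 0.885 | 1.5 points |
| 0.60 | 0.85 × 0.90 + 0.15 × 0.60 = 0.855 | 4.5 points |
| 0.40 | 0.85 × 0.90 + 0.15 × 0.40 = 0.825 | 7.5 points |

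Letting *d* run from 0.05 (6 people) to 0.30 (36 people) over the same *p_l* widens the range. The smallest gap is 0.05 × (0.90 − 0.80) = 0.5 points and the largest is 0.30 × (0.90 − 0.40) = 15 points. If *p_l* = *p_h*, the gap is zero whatever *d* is.

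**The case against.** Four points can be made for the plan.

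- **Focus groups are not the only evidence.** Attendance and drop-out are recorded for the whole arm, so heavy drop-out would be visible beside favourable themes. This stands. The counts cannot separate leaving because of transport or illness from leaving because the content was disliked, so they do not replace asking.
- **Leavers are not excluded.** A reader might infer that only satisfied completers will be heard. The documents do not say so: the reunion is for the workshop group as a whole, and the focus groups are with participants, without further restriction. Invitations may already go to everyone. This stands too. However, being eligible for a reunion is not the same as attending it, and no step is described to bring in those who stopped.
- **There is no rate to inflate.** A reader might infer that acceptability will be overstated by some number of points. The focus groups produce themes and not a percentage, so that reading attaches a bias to an estimate the plan never makes. This stands. In practice the effect would be missing or under-represented themes.
- **Focus groups normally involve a subset, and one example question in the guide asks for suggested improvements.** Both are true. A subset is no fault in itself. The difficulty is that the only source of opinions is a subset likely to be selected on engagement.

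**Conclusion.** The concern holds in a limited form. The plan sets out to determine acceptability among 120 recipients, but asks for opinions only in focus groups tied to a later reunion, has no survey item on acceptability, and describes no route to people who left. The conclusion may therefore be more favourable than the view of all recipients and may miss reasons for stopping.

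That reunion attenders are the more engaged is an inference from the event's purpose and timing; the documents do not state it. They do not support saying that acceptability certainly will be overstated, or that leavers are shut out. The range of 1.5 to 7.5 points at 15% unheard shows what could happen under assumed inputs and is not an estimate for this trial. This is a worthwhile, inexpensive improvement to one aim and leaves the efficacy analysis as it is.

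**What to change.** 1. Add three or four items on acceptability and, where relevant, the reason for stopping to the 3-month survey. Send it to everyone randomised to the workshop, whether or not they completed the program. The survey already goes to this arm with reminders, a $20 gift card, and phone or paper for those who cannot complete it online.
2. Report these items against all 120, with the number of non-respondents shown, beside the attendance and attrition data.
3. Invite focus-group members from the full workshop list, including those who stopped attending, and state this in Procedures.

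The cost is a slightly longer survey and a minor ethics amendment. Non-response among leavers will remain, but it can be counted and bounded. For example, suppose 18 of 120 did not answer and 90% of the other 102 were favourable (both assumed). The share among all 120 would then lie between 0.85 × 0.90 = 76.5%, if no non-respondent were favourable, and 0.85 × 0.90 + 0.15 = 91.5%, if all were.
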